### 9.3 Handling of the Difference between the Scheduled and the Actual Sampling Times

The actual clock time for patch application and each collection time for the PK samples will be

This document is confidential.

Version: Draft 0.2, 21-Sep-2021

Controlled Document ID: 2805A.00, Effective Date 29-Jul-2019

Filing requirements: TMF Page 22 of 37

GSK Consumer Healthcare

recorded. For all sampling times, the actual sampling times relative to patch application will be calculated as the difference between the actual clock time of sampling and the actual clock time of patch application. The actual post-dose sampling times relative to patch application expressed in hours and rounded off to three decimal digits will be used to calculate the PK parameters, except for pre-dose samples occurring prior to patch application, which will always be reported as zero (0.000), regardless of the time difference. Scheduled sampling times will be presented in concentration tables and mean graphs, while actual sampling times will be presented in the individual graphs.

### 9.4 PK Sampling Schedule

Blood samples will be collected from each subject during this study for the determination of the PK of nicotine.

PK blood samples of nicotine will be drawn according to the following schedule (acceptable tolerance window):

Predose (within 1 hour before patch application) and at 30 minutes and at 1, 2, 3, 4, 5, 6, 8, 10, 12, 14, 16, 18, 20, 24, 25, 26, 27, 28, 30, 32, and 36 hours after administration of the patch.

Timepoints defined as minor protocol deviations due to sampling window times, only, will not be considered protocol deviations for the analysis of the PK Population.

#### 9.5 Plasma Pharmacokinetic Parameters

Plasma concentrations from nicotine will be used to calculate the following parameters by standard non-compartmental methods for Part A, B, and C (Day 1):

PK Parameter	Definition		
	Primary PK Parameters		
AUC 0-t	Area under the plasma concentration versus time curve from time zero to time t, where t is the time of the last measurable plasma concentration of nicotine, estimated, computed using the linear trapezoidal rule		
AUC 0-inf	Area under the plasma concentration versus time curve calculated from time zero to infinity. $AUC_{0-inf} = AUC_{0-t} + C(t)/\lambda_z$ where $C(t)$ is the concentration at the last measurable sampling time point and $\lambda_z$ is the terminal elimination rate constant)		
C max	The highest observed plasma nicotine concentration		
Secondary PK Parameters			
t max	Time to maximum plasma nicotine concentration		
t½	Apparent elimination half-life, calculated as ln(2)/λz		
$\lambda_z$	Apparent elimination rate constant for plasma nicotine computed as the slope		

This document is confidential.

Version: Draft 0.2, 21-Sep-2021

Controlled Document ID: 2805A.00, Effective Date 29-Jul-2019

GSK Consumer Healthcare

PK Parameter	Definition
	of the regression line of ln (C(t)) on time.

-The linear trapezoidal method will be employed for all incremental trapezoids arising from increasing concentrations and the logarithmic trapezoidal method will be used for those arising from decreasing concentrations.

- \(\lambda\)z will be estimated at terminal phase by linear regression after log-transformation of the concentrations.
- -Only those data points that are judged to describe the terminal log-linear decline will be used in the period after regression.
- -A minimum number of 3 data points in the terminal phase will be used in calculating  $\lambda_z$  with the line of regression starting at any post- $C_{max}$  data point ( $C_{max}$  will not be part of the regression slope). The adjusted coefficient of determination ( $R^2$  adjusted) in general should be greater than 0.80. All the derived parameters (e.g.,  $\lambda_z$ ,  $t_{\%}$ , AUC0-inf) will be flagged accordingly. The time point where ln-linear  $\lambda_z$  calculation begins ( $\lambda_z$  lower), the actual sampling time of the last quantifiable concentration used to estimate the  $\lambda_z$  ( $\lambda_z$  upper) as well as the  $R^2$  adjusted for the ln-linear regression for the calculation of the elimination rate constant calculation will be reported.
- -An appropriate number of decimal places will be used for  $\lambda_z$  to enable the reported value of  $t_{\frac{1}{2}}$  to be calculated.

### 9.6 Statistical Analyses

Individual plasma concentrations will be listed and summarized descriptively at each time point; the concentration vs. time profile will be graphed by formulation for individual subjects and for the arithmetic mean (±SD) on both original and logarithmic scales with Safety population. For ease of presentation, actual and scheduled sampling times will be used to present results for individual and mean figures respectively.

The PK parameters (AUC0-t, AUC0-inf, and Cmax) will be summarized for each treatment by descriptive statistics for each study treatment.

The parameters  $\lambda_z$ ,  $t_{1/2}$  and  $t_{max}$  will be summarized by descriptive statistics (mean, median, Q1, Q3, minimum, maximum, standard deviation, and coefficient of variation) for each study treatment.

#### 9.7 Assessment of Bioequivalence

The primary objective will be evaluated based on the following comparison:

The nicotine 21 mg patch manufactured at Alza (Reference) versus the 21 mg patch manufactured at GSKCH Dungarvan (Test), in terms of nicotine AUC0-t, AUC0-inf and Cmax.

A linear mixed effects model will be fit to the log-transformed PK variables (AUC $_{0-t}$ , AUC $_{0-inf}$  and C $_{max}$ ), as the dependent variable, and treatment, and period as fixed effects. Subject nested within sequence will be a random effect. Least squares estimates of treatment effects will be

This document is confidential.

Version: Draft 0.2, 21-Sep-2021

Controlled Document ID: 2805A.00, Effective Date 29-Jul-2019

Filing requirements: TMF Page 24 of 37

GSK Consumer Healthcare

calculated and a 90% confidence interval (CI) for the treatment difference will be computed. The treatment difference and its CI will be exponentiated to obtain the ratio of the geometric means between the test and reference products (test/reference) and its CI.

Bioequivalence between the test and reference treatments (on baseline-adjusted data) will be concluded if the 90% confidence interval for the ratio of the means for each of the PK parameters AUC0-t, AUC0-inf, and Cmax of the nicotine profiles lie entirely within the interval 0.8 to 1.25.

The SAS code for the analysis model will follow the format given below (The input variables (or datasets) are depicted in slanted red text and have been given generic names).

If the study is dosed in groups due to enrollment issues, the following terms will be included in the model: group, period within group, treatment, and treatment by group. If the term of treatment by group was found to be not statistically significant (i.e. p>0.05), then the treatment by group term specified in the previous model would be removed from the model to calculate the ratio and 90% CI for AUC0-t, AUC0-inf and Cmax as applicable.

### 9.8 Non-parametric Assessment of PK Parameters

A nonparametric analysis will be performed to compare study treatments using the Wilcoxon Signed Rank Test for the PK parameters  $t_{max}$ ,  $t_{1/2}$ , and  $\lambda_z$ . Median difference, 95% confidence interval of Hodges-Lehmann's median estimate, and p-value will be presented.

If the P-value is significant at the 5% level, then PK parameter values are considered unequal across all dose levels. If the P-value is not significant, then PK similarity may be suggested across the investigated products.

The SAS code to perform the test will follow the format given below (using the univariate Procedure). The input variables, datasets and labels are depicted in slanted red text and have been given generic names.

This document is confidential.

Version: Draft 0.2, 21-Sep-2021

Controlled Document ID: 2805A.00, Effective Date 29-Jul-2019

GSK Consumer Healthcare

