### Analyses

The primary objective will be evaluated based on the following comparison:

The nicotine 21 mg patch manufactured at Alza (Reference) versus the 21 mg patch manufactured at GSKCH Dungarvan (Test), in terms of nicotine  $AUC_{0-t}$ ,  $AUC_{0-inf}$  and  $C_{max}$ .

The statistical analyses will be done based on PK analysis set, (see [section 12.2](#) for definition). Safety population will be used for individual plasma concentration listings and figures.

A linear mixed effects model will be fit to the log-transformed PK variables ( $AUC_{0-t}$ ,  $AUC_{0-inf}$  and  $C_{max}$ ), as the dependent variable, and treatment, and period as fixed effects. Subject nested within sequence will be a random effect. Least squares estimates of treatment effects will be calculated and a 90% confidence interval (CI) for the treatment difference will be computed. The treatment difference and its CI will be exponentiated to obtain the ratio of the geometric means between the test and reference products and its CI.

Bioequivalence between the test and reference treatments (on baseline-adjusted data) will be concluded if the 90% confidence interval for the ratio of the means for each of the PK parameters  $AUC_{0-t}$ ,  $AUC_{0-inf}$ , and  $C_{max}$  of the nicotine profiles lie entirely within the interval 0.8 to 1.25.

The PK parameters ( $AUC_{0-t}$ ,  $AUC_{0-inf}$ , and  $C_{max}$ ) will be summarized for each treatment by descriptive statistics (N, arithmetic mean, standard deviation, geometric mean, coefficient of variation, median, minimum, and maximum). A listing containing individual and summary statistics for each PK parameter will be provided. A similar listing will be provided for log and linear plasma concentrations over time containing individual values and summary statistics for each time point.

Individual plasma concentrations will be listed and summarized descriptively at each time point; the concentration vs. time profile will be graphed by formulation for individual subjects and for the mean on both original and logarithmic scales with Safety population.

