#### **12.3.2 Secondary Analysis(es)**

The PK analysis set will be used for the secondary analysis.

For each study product, the following pharmacokinetic parameters will be estimated:

$t_{max}$  time to maximum plasma nicotine concentration;

$t_{1/2}$  apparent elimination half-life;

$\lambda_z$  apparent elimination rate constant for plasma nicotine computed as the slope of the regression line of  $\ln(C(t))$  on time. The regression should generally involve at least 3 consecutive measurable concentrations that decrease over time.

The parameters  $\lambda_z$  and  $t_{1/2}$  and  $t_{max}$  be summarized (mean, median, Q1, Q3, minimum, maximum, standard deviation, and coefficient of variation) for each study treatment. A nonparametric analysis will be performed to compare study treatments using the Wilcoxon Signed Rank Test. Median difference, 95% confidence interval and p-value will also be presented.

Additional PK parameters or statistical analyses may be performed as appropriate.

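### The signed-rank comparison of tmax, half-life and λz has no period term, so if a period effect exists it loses power with equal sequences and its Hodges-Lehmann estimate is off-centre with unequal ones

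*SAP*

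**What the plan says.** The trial is a two-sequence, two-period crossover. For the primary parameters, SAP 9.7 fits a mixed model to the log-transformed values: "as the dependent variable, and treatment, and period as fixed effects. Subject nested within sequence will be a random effect". Protocol 12.3.1 has the same fixed effects, "treatment, and period as fixed effects".

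For tmax, half-life and λz the method changes. Protocol 12.3.2 says "A nonparametric analysis will be performed to compare study treatments using the Wilcoxon Signed Rank Test". SAP 9.8 repeats this and goes on to list the three parameters: "A nonparametric analysis will be performed to compare study treatments using the Wilcoxon Signed Rank Test for the PK parameters". It adds the software ("using the univariate Procedure") and the output: a median difference, then "95% confidence interval of Hodges-Lehmann's median estimate, and p-value will be presented". Neither section mentions period, sequence or a period-adjusted difference.

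SAP 9.8 also says how the result will be read. On one side: "If the P-value is significant at the 5% level, then PK parameter values are considered unequal across all dose levels". On the other: "If the P-value is not significant, then PK similarity may be suggested across the investigated products".

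The analysis set is built from subjects who completed both periods (SAP 6.2). The plan allows for a 40% loss, from 20 subjects to 12 (SAP 5.2).

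**The concern.** A one-sample signed-rank test on Test minus Reference treats all within-subject differences as draws from one distribution. In a crossover that holds only if there is no period effect. Otherwise the effect enters the differences with opposite signs in the two sequences. With equal sequence sizes this cancels in the centre but widens the spread. With unequal sizes it does not cancel, and the centre moves.

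The plan makes allowance for period on AUC and Cmax, and gives no reason for not doing so on parameters taken from the same concentration profiles.

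Two outputs are at stake. One is the reported median difference and its 95% interval. The other is the statement about PK similarity, which SAP 9.8 attaches to a non-significant p-value. A test that has become conservative leans toward that statement.

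**Working it through.** **Inputs from the documents.** Two sequences and two periods. 20 subjects randomised, 12 completers, 40% loss (SAP 5.2). Block randomisation, with ratio and block size not stated (SAP 5.3). A 5% level for the secondary test (SAP 9.8), taken as two-sided.

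**Assumptions.** 10:10 allocation; normal paired differences; true treatment shift τ; period effect π (Period 2 minus Period 1). Both τ and π are in units of the SD of the within-subject difference. The documents give no value for either, so a range is shown for π.

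**The plan's own figure.** 12 / (1 − 0.40) = 20, which matches the stated number enrolled. The documents state no power for the signed-rank test.

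**Mechanism.** Test minus Reference centres on τ − π in the sequence Test-then-Reference (TR) and on τ + π in Reference-then-Test (RT). The mean of the pooled differences is therefore off by

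π × (n_RT − n_TR) / N.

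For 7:5 and π = 0.5 this is 0.5 × (5 − 7) / 12 = −0.083. For 8:4 and π = 0.5 it is 0.5 × (4 − 8) / 12 = −0.167. With equal sequences it is zero.

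Period 1 minus Period 2 centres on τ − π in TR and on −τ − π in RT. The gap between the sequences is 2τ, and π drops out. Half of that gap is the treatment difference.

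**How likely are unequal sequences?** If 8 of 20 are lost at random from 10:10:

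- P(6:6) = C(10,4)² / C(20,8) = 44,100 / 125,970 = 0.35
- P(7:5) = 2 × C(10,3) × C(10,5) / C(20,8) = 60,480 / 125,970 = 0.48
- P(8:4 or worse) = 1 − 0.35 − 0.48 = 0.17

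So P(unequal) = 0.65.

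**Power at τ = 1 SD.** Exact tests, simulated; repeat runs agree to about 0.01.

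| Completers | π | Signed-rank | Period-adjusted rank-sum |
|---|---|---|---|
| 6:6 | 0 | 0.85 | 0.83 |
| 6:6 | 0.25 | 0.83 to 0.84 | 0.83 |
| 6:6 | 0.5 | 0.77 to 0.78 | 0.83 |
| 6:6 | 1 | 0.52 | 0.82 to 0.83 |
| 7:5 | 0.25 | 0.80 | 0.83 to 0.84 |
| 7:5 | 0.5 | 0.69 to 0.70 | 0.83 |
| 8:4 | 0 | 0.85 to 0.86 | 0.80 |
| 10:10 | 0.5 | 0.97 | 0.98 |

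**Rejection rate with no treatment difference, 6:6.** Signed-rank: 0.042, 0.024 and 0.005 at π = 0, 0.5 and 1. Rank-sum: about 0.04 throughout.

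**Size of the bias in the Hodges-Lehmann estimate (SD units).**

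| Completers | π | Formula for the mean | Simulated Hodges-Lehmann |
|---|---|---|---|
| 7:5 | 0.25 | 0.042 | 0.04 |
| 7:5 | 0.5 | 0.083 | 0.08 to 0.09 |
| 7:5 | 1 | 0.167 | 0.18 |
| 8:4 | 0.25 | 0.083 | 0.08 to 0.09 |
| 8:4 | 0.5 | 0.167 | 0.17 |
| 8:4 | 1 | 0.333 | 0.37 |

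Half the between-sequence Hodges-Lehmann shift has a bias of about zero in every scenario.

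**The case against.** The strongest reply is that the documents show no period effect in these parameters, and that a period term in the primary model is not evidence of one. Conditions are standardised through confinement, fasting, set meals and abstinence. With no period effect the signed-rank test is unbiased and slightly more powerful. This stands: both harms are conditional.

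A period effect of 1 SD is also large. If the 13% intra-subject CV applied to half-life (an assumption), the SD of a paired log difference would be about 0.13 × √2 = 0.18. One SD would then be a shift of roughly 20% between patches applied four days apart on the planned schedule. The 1 SD rows are best read as an upper end.

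Readers might draw four stronger conclusions that the documents do not support:

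- *That the estimate is biased whenever sequences are unequal.* It is biased only if π is not zero.
- *That false-positive findings increase.* They did not in these runs. At 8:4 with π = 1 SD and no treatment difference, the rejection rate was about 0.04.
- *That the displacement at 8:4 and 1 SD is 0.45 SD.* That figure belongs to the raw sample median. The Hodges-Lehmann estimate, to which the SAP's interval refers, is off by about 0.37 SD.
- *That the trial's conclusion is pushed toward equivalence.* It rests on 90% intervals for AUC0-t, AUC0-inf and Cmax from a model that includes period.

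Reading a non-significant result as similarity is a separate weakness. The fix here does not cure it: at 6:6 the rank-sum test still misses a true 1 SD shift about 17% of the time (1 − 0.83).

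**Conclusion.** The point holds in conditional form, as a low-cost improvement to a secondary analysis. The specified test omits a factor that the plan's own primary model includes. If that factor matters, the cost is lost power at equal sequences and a displaced estimate and interval at unequal ones. On the stated assumptions, unequal sequences are the likelier outcome (0.65), and 7:5 is the commonest split.

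At a moderate period effect of 0.5 SD, power falls from 0.85 to 0.77 or 0.78 at 6:6, and is 0.69 to 0.70 at 7:5, where the estimate is off by about 0.09 SD. At 0.25 SD or less, the harm is negligible at equal sequences and small at 7:5.

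There are two limits. The simulations use continuous normal data, whereas tmax falls on scheduled sampling times and will have ties; the power figures are therefore less certain for tmax, although the bias mechanism does not depend on this. The SAS code for SAP 9.8 is not in the text available for review, so its input variable could not be checked; the prose describes no period-adjusted input.

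Only tmax, half-life, λz and the similarity statement are affected.

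**What to change.** In SAP 9.8, replace the signed-rank test with a comparison of within-subject Period 1 minus Period 2 differences between the two sequences. Use the exact Wilcoxon rank-sum test, and state how ties will be handled for tmax. Report half the Hodges-Lehmann shift and half each limit of its 95% interval as the treatment difference, with the direction (Test minus Reference) stated.

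Because protocol 12.3.2 names the signed-rank test, record the change in SAP section 11, which currently reports no changes from the protocol.

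This takes a sentence or two in the SAP and a short code change, and needs no new data. The statistical price is slightly lower power when there is no period effect: 0.83 against 0.85 at 6:6, and about 0.80 against 0.85 to 0.86 at 8:4.

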### 5.2 Determination of Sample Size

Twenty (20) healthy adult smokers will be enrolled in the study, to ensure that 12 complete the entire study assuming a 40% dropout and non-evaluable rate. The highest intra-subject CV calculated from previous studies was 13%.

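### SAP 9.8 tests t½ and λz separately, each with its own verdict, although one is ln(2) over the other, so the same data can give one quantity opposite verdicts.

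*SAP*

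**What the plan says.** Protocol 12.3.2 plans the comparison for the secondary parameters λz, t½ and tmax: "A nonparametric analysis will be performed to compare study treatments using the Wilcoxon Signed Rank Test", with a median difference, a 95% confidence interval and a p-value. It gives no rule for reading the p-value.

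SAP 9.8 repeats the test for the same three parameters, specifies the "95% confidence interval of Hodges-Lehmann's median estimate, and p-value will be presented", and adds a two-way rule. On one side: "If the P-value is significant at the 5% level, then PK parameter values are considered unequal across all dose levels". On the other: "If the P-value is not significant, then PK similarity may be suggested across the investigated products".

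SAP 9.5 defines t½ as "Apparent elimination half-life, calculated as ln(2)/λz", and SAP 4.1 gives the same relation. SAP section 11 reports no change in planned analyses from the protocol. Bioequivalence (SAP 9.7) rests only on the 90% intervals for AUC0-t, AUC0-inf and Cmax.

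**The concern.** Once a subject's λz is known, t½ is known exactly. A comparison of elimination between the two patches therefore has one answer, but SAP 9.8 asks the question twice on two scales and draws a conclusion each time. The signed-rank test is not invariant to a reciprocal, so the report could call half-life unequal while suggesting similarity for λz, or the reverse. No rule says which prevails. What is at stake is the secondary objective of assessing the pharmacokinetic profile.

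The verdict wording has two further faults. It refers to all dose levels in a trial with a single 21 mg strength. It also reads a non-significant result as a sign of similarity, which a test of difference in 12 to 20 subjects cannot support.

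**Working it through.** **Inputs from the documents.** 5% per test (SAP 9.8). t½ = ln(2)/λz (SAP 9.5). Number of pairs: SAP 5.2 enrols 20 "to ensure that 12 complete the entire study assuming a 40% dropout and non-evaluable rate", and 12/(1 − 0.40) = 20 reproduces that figure. The PK population needs both periods (SAP 6.2), so there are about 12 to 20 pairs.

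**Inputs assumed.** A two-sided exact test (sidedness is not stated; the 95% interval suggests two-sided). Raw differences, inferred from the median-difference wording, because the SAS code that SAP 9.8 refers to is not visible in the available text. Log-normal λz. The variability of λz is not given: the only CV, 13%, names no parameter.

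**Why the two tests differ.** For one subject,

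λz,T − λz,R = ln(2) × (1/t½,T − 1/t½,R) = −ln(2) × (t½,T − t½,R)/(t½,T × t½,R).

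Every sign reverses, which alone would leave a two-sided p-value unchanged. But each difference is also divided by that subject's own product of half-lives, so the ranks of the absolute differences change. On the log scale, ln(λz,T/λz,R) = −ln(t½,T/t½,R): the absolute values are identical, and so is the p-value.

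**Worked example.** Twelve simulated subjects with half-lives within the 1 to 4 h of Protocol 4.2. The set was chosen because the tests disagree, so it shows what is possible, not how often.

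| t½ T | t½ R | t½ diff | rank | λz diff | rank | log-ratio rank |
|---|---|---|---|---|---|---|
| 3.39 | 3.10 | +0.29 | 5 | −0.019 | 2 | 2 |
| 2.37 | 1.29 | +1.08 | 11 | −0.245 | 12 | 12 |
| 1.47 | 1.74 | −0.27 | 3 | +0.073 | 6 | 5 |
| 3.81 | 2.77 | +1.04 | 10 | −0.068 | 4 | 9 |
| 1.07 | 1.22 | −0.15 | 2 | +0.080 | 7 | 3 |
| 2.90 | 2.47 | +0.43 | 7 | −0.042 | 3 | 4 |
| 1.52 | 1.80 | −0.28 | 4 | +0.071 | 5 | 6 |
| 1.55 | 1.17 | +0.38 | 6 | −0.145 | 11 | 8 |
| 2.56 | 1.69 | +0.87 | 9 | −0.139 | 10 | 11 |
| 3.79 | 2.56 | +1.23 | 12 | −0.088 | 8 | 10 |
| 4.00 | 3.93 | +0.07 | 1 | −0.003 | 1 | 1 |
| 1.99 | 1.53 | +0.46 | 8 | −0.105 | 9 | 7 |

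The smaller rank sum comes from the third, fifth and seventh subjects.

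- t½: 3 + 2 + 4 = 9, exact p = 66/4096 = 0.016, read as unequal.
- λz: 6 + 7 + 5 = 18, exact p = 450/4096 = 0.110, read as similarity.
- Log ratio: 5 + 3 + 6 = 14, exact p = 214/4096 = 0.052, the same for both parameters.

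**How often.** Paired log-normal simulation with 12, 16 and 20 pairs.

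- *Identical products*, between-subject log SD 0.3 to 0.5, within-subject log SD 0.13 to 0.35: opposite verdicts in about 2.5 to 4.4% of trials, which is 45 to 63% of the trials in which either test is significant. A milder set (between-subject CV 20 to 40%, within-subject CV 10 to 30%) gives 1.9 to 3.8%, or 36 to 57%.
- *True log difference 0.2*, first set of SDs: about 1 to 16% of trials, with one 16-pair setting at 17%. At SDs of 0.4 and 0.25 it is 14 to 15%. The low end is where both tests almost always reject.
- *Power at SDs of 0.4 and 0.25*: the log-ratio test gives 0.39 against 0.37 for either raw test at 12 pairs, and 0.65 against 0.61 to 0.62 at 20 pairs.

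**Level of each test.** The exact size of one signed-rank test at 5% is 4.25%, 4.43% and 4.84% for 12, 16 and 20 pairs. None exceeds the stated level.

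**The case against.** A reader might infer that three unadjusted tests break a 5% error rate. With no product difference and tmax roughly independent of elimination, the chance of at least one unequal verdict is indeed about 9 to 12%. The documents do not support calling this a breach. SAP 9.8 sets 5% for each parameter, states no family rate and does not combine the three results. Nor is the duplicate the main source: tmax plus a single elimination test, if independent, still gives 1 − (1 − 0.0425)² = 8.3% at 12 pairs and 1 − (1 − 0.0484)² = 9.5% at 20. Two parameters each tested at 5% is ordinary for secondary pharmacokinetics.

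A reader might also want a Holm adjustment. It would reduce first-step power at the alternative above from 0.39 to about 0.27 or 0.28 (12 pairs) and from 0.65 to 0.53 (20 pairs). While a non-significant result is read as similarity, it would make that reading easier to reach.

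Two other objections stand as qualifications. The raw scale is inferred. And the figure of roughly half is conditional on a significant result; with identical products, the unconditional rate is only a few per cent. Neither removes the point, because that opposite verdicts are possible follows from the definitions and only the frequency depends on assumed variability.

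**Conclusion.** The point holds as a defect in the secondary analysis. SAP 9.8 can return opposite verdicts on one quantity, in about 2 to 4% of trials with identical products and about 1 to 16% at a true log difference of 0.2 (17% in one setting). These figures rest on the assumed log SDs, exact two-sided tests and raw differences.

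It does not inflate any stated error rate, and it does not touch the bioequivalence conclusion, which uses other parameters and a different method. It is a cheap improvement, best made while the SAP is still marked as a draft.

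**What to change.** In SAP 9.8:

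1. Base the elimination comparison on one signed-rank test of ln(λz,T/λz,R). Report the one p-value for both parameters, with reciprocal ratio estimates.
2. Keep the protocol-planned median difference and 95% interval for t½ and for λz, labelled descriptive. These intervals are on the raw scales, so one may exclude zero when the other does not. State that the log ratio is the comparison.
3. Delete both verdict sentences, and treat the tmax and elimination p-values as descriptive. No Holm adjustment is then needed.
4. Record the change in SAP section 11, or align Protocol 12.3.2.

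The cost is wording and a log transform in one program, with no new data. The small downside is that t½ and λz no longer have separate p-values. In the settings simulated, the log-ratio test loses no power against either raw test.

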## 12 STATISTICAL CONSIDERATIONS AND DATA ANALYSES

### 12.1 Sample Size Determination

A sufficient number of healthy adult smokers will be screened to randomize approximately 20 healthy adult smokers, to ensure that 12 complete the entire study assuming a 40% dropout and non-evaluable rate. The highest intra-subject CV calculated from previous studies was 13%.

CCI

[REDACTED]

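### SAP 9.8 lets a non-significant Wilcoxon test on tmax, t1/2 or λz suggest PK similarity with no margin, so small or noisy data favour that reading

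*SAP*

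**What the plan says.** SAP 9.8 applies a Wilcoxon signed-rank test to tmax, t1/2 and λz and reports a median difference, a 95% confidence interval for the Hodges-Lehmann estimate, and a p-value. It then says how to read the p-value in each direction. If it is significant at 5%, "then PK parameter values are considered unequal across all dose levels". For the other outcome: "If the P-value is not significant, then PK similarity may be suggested across the investigated products".

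The primary analysis works differently. Under SAP 9.7, bioequivalence requires the 90% CI for each of AUC0-t, AUC0-inf and Cmax to "lie entirely within the interval 0.8 to 1.25".

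Protocol 12.3.2 plans the same signed-rank test ("Median difference, 95% confidence interval and p-value will also be presented") but gives no rule for reading a non-significant result. That rule appears only in the SAP. Protocol 12.3 allows the SAP to add detail, so this is not a breach, but nothing in the protocol requires the sentence.

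**The concern.** A non-significant test can mean that the products are alike or that the data cannot tell. SAP 9.8 reads both cases the same way. It sets no limit on the Hodges-Lehmann interval and does not tie the similarity reading to it, so the reading depends on the p-value alone. Losing subjects or gaining noise then makes the favourable statement easier to reach. In SAP 9.7 the effect is the opposite: poor precision widens the interval and makes the claim harder.

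At stake is the secondary objective of assessing the PK profile of the patches. The report could suggest similar half-life, elimination rate or tmax only because the data were imprecise.

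The preceding sentence, on a significant result, is ordinary in substance. Its defect is editorial: it refers to dose levels, and this study has one strength and two products.

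**Working it through.** **Inputs from the documents**

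- Sample size: protocol 12.1 plans about 20 randomized "to ensure that 12 complete the entire study assuming a 40% dropout and non-evaluable rate". Check: 12 / (1 − 0.40) = 20, which reproduces the plan's figure.
- Variability: SAP 5.2 gives one value, "The highest intra-subject CV calculated from previous studies was 13" per cent, without naming the parameter.
- Margin for tmax, t1/2 or λz: none in either document.
- Power for these parameters: none in the visible text. Part of protocol 12.1 is redacted, so what it may say cannot be checked.

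**Assumptions**

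- Two-sided exact test at 5%.
- Log-normal t1/2, no ties, no period effect.
- Within-subject CV of 13%, 20% or 30%. Only 13% appears in the documents, and not for a named parameter.

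**Formulas**

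- Log-scale SD per period: s = √ln(1 + CV²).
- SD of the within-subject difference: s√2.
- Standardized shift: d = ln(true ratio) / (s√2).

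For a true ratio of 1.25, ln(1.25) = 0.223:

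- CV 13%: s√2 = 0.183, d = 1.22
- CV 20%: s√2 = 0.280, d = 0.80
- CV 30%: s√2 = 0.415, d = 0.54

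**Critical values.** The exact test rejects when the smaller rank sum is at most 13 with 12 subjects (true size 4.2%) and at most 52 with 20 subjects (true size 4.8%).

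**Chance of a non-significant result** (200,000 simulated trials per cell):

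| True ratio | n | CV 13% | CV 20% | CV 30% |
|---|---|---|---|---|
| 1.25 | 12 | 4.5% | 33.6% | 64.3% |
| 1.25 | 20 | 0.1% | 9.1% | 39.9% |
| 1.10 | 12 | 66.1% | 83.5% | 90.3% |
| 1.10 | 20 | 42.3% | 71.1% | 84.4% |

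As calibration, at a true ratio of 1.00 the result is non-significant in 95.8% of trials at n = 12 and 95.1–95.2% at n = 20, in line with the test sizes.

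The visible text of SAP 9.8 states no log transformation. On untransformed t1/2 differences, with an assumed between-subject CV of 30%, the 1.25 rows become 5.4 / 35.5 / 65.6% (n = 12) and 0.15 / 10.4 / 42.1% (n = 20). The choice of scale hardly matters.

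**Contrast with a margin.** For illustration only, suppose t1/2 were judged by a 90% CI within 0.80–1.25. At a true ratio of 1.25 and n = 12, the chance of a similarity reading would be 4.9 / 4.9 / 3.4% at the same three CVs. It does not rise as precision worsens.

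**The other two parameters.** SAP 9.5 defines t1/2 as "Apparent elimination half-life, calculated as ln(2)/λz", so λz carries the same information and is not a second illustration. No rate is given for tmax. It is read off the sampling grid ("16, 18, 20, 24, 25, 26, 27, 28, 30, 32, and 36 hours after administration of the patch"), which has a 4-hour gap between 20 and 24 h, so ties are likely and continuous data cannot be assumed. Zero differences would reduce the number of informative pairs. With five such pairs the smallest two-sided p-value is 2/2⁵ = 0.0625, so with five or fewer the test cannot reach 5% and the similarity reading would be automatic.

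**The case against.** The strongest case on the other side concerns weight. The statement is hedged, whereas SAP 9.7 sets a confirmatory rule. Study success is defined in protocol section 3 by AUC0-t, AUC0-inf and Cmax only. The Hodges-Lehmann interval is shown beside the p-value, so a reader can see imprecision. All of this stands, and it is why the point is modest. It does not make the inference valid.

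The size also depends on assumed CVs. At 13%, the only documented value, a true 25% difference is missed in about 4.5% of trials at n = 12, close to the 4.9% for the illustrative margin rule. That is correct. But nothing in the documents says that 13% applies to t1/2, and the safeguard disappears as the CV rises. Twelve is also the planned minimum, not the expected number; the figures for 20 are given for that reason.

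The 10% rows should not be counted as wrong readings, because a ratio of 1.10 lies inside 0.8–1.25, the only limits in the documents. That is fair. They show only how often the test is silent about a moderate difference.

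The SAS code mentioned in SAP 9.8 is absent from the public text, so a transformation specified there cannot be ruled out. The check on both scales shows that it would make little difference.

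Finally, keeping the significance sentence while removing the other may look one-sided. It is not inconsistent: rejecting equality supports a difference, while failing to reject does not support similarity. The importance of a difference must still be read from the interval.

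**Conclusion.** The concern holds: the non-significance sentence in SAP 9.8 is wrong as written. The direction of the fault needs no assumed CV: without a margin, weaker data favour the similarity reading.

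Its size does depend on the CV. If the CV of t1/2 is about 20%, the plan's own allowance for loss from 20 to 12 subjects raises the chance of the similarity reading under a true 25% difference from about 9% to about 34%. If it is 13%, the rise is from about 0.1% to about 5%. Both statements rest on the log-normal, no-ties and no-period-effect assumptions above and concern t1/2 (equivalently λz), not tmax.

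The primary bioequivalence conclusion is unaffected. The sentence should be changed because it governs what the report may say about a stated secondary objective.

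**What to change.** In SAP 9.8, delete the sentence on a non-significant p-value and put in its place: *Interpretation rests on the Hodges-Lehmann estimate and its 95% CI; no conclusion of similarity is drawn from a non-significant p-value.* Keep the sentence on a significant p-value, but replace its reference to dose levels with *between the two products*.

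Every output planned in protocol 12.3.2 stays, and the interval is already planned, so there is no new analysis. The SAP shown is Draft 0.2, so the edit is simple. The cost is that the report loses a hedged similarity statement on secondary parameters.

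Setting a margin instead would also be valid, but the documents give no basis for choosing one. With 12 subjects it could be hard to meet: under the illustrative 0.80–1.25 rule and an assumed CV of 30%, truly identical products would pass in only about 16% of trials.
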